16.2.2. Methods of Analysis

Statistical analyses will be [REDACTED] and descriptive in nature, with appropriate measures of precision provided where applicable. There is no planned statistical hypothesis testing in this study.

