4 SAMPLE SIZE JUSTIFICATION

The sample size for this study is not based on formal hypothesis testing but on the precision of the estimation of the primary endpoints and the ratios between various ALC subgroups.

For example, the Phase 2 and 3 controlled and uncontrolled efficacy and safety studies in MS, based on data available as of May 2014 from 2470 subjects with at least 1 post-Baseline value from the interim analysis of the Integrated Summary of Safety of Tecfidera, showed that 76% of subjects had all ALC values \geq LLN and 24% had at least 1 ALC value $<$ LLN up to Week 48. Assuming the same proportion of subjects in this study will have 1 or more ALC values $<$ LLN, it is expected that approximately 137 subjects will have all ALC values \geq LLN and approximately 43 subjects will have at least 1 ALC value $<$ LLN at Week 48, based on a total of 180 evaluable subjects at Week 48. With this sample size, the 90% CIs for the ratio of the 2 subgroups for the change from Baseline at Week 48 in lymphocyte subsets are illustrated below using the scenario of a true ratio of 0.8 (20% decrease) and 0.7 (30% decrease), respectively. When assessing lymphocyte subsets between subjects with at least 2 ALC values $<$ LLN up to the first 48 weeks of treatment versus subjects who have all ALC values \geq LLN throughout the study, the 90% CIs of the ratio would be wider, as historical data suggest that 16% of the patients treated with Tecfidera may have 2 or more ALC values $<$ LLN during the first 48 weeks of treatment.

To allow for a 10% discontinuation rate, a total of 200 subjects are planned for enrollment.

Table 3: Sample Size Calculations

Primary Endpoints	SD ^{a)}	Ratio	90% CI for the Ratio Based on N = 180	
			Subjects With At Least 1 ALC $<$ LLN ^{b)} vs. Subjects With All ALC \geq LLN ^{b)}	Subjects With At Least 2 ALC $<$ LLN ^{b)} vs. Subjects With All ALC \geq LLN ^{b)}
	0.32	0.8	0.73, 0.88	0.71, 0.90

CONFIDENTIAL

The information contained herein may not be used, disclosed, or published without the written consent of Biogen Idec MA Inc.

biogen idec	Protocol 109MS310 An Open-Label Study to Assess the Effects of BG00012 on Lymphocyte Subsets in Subjects With RRMS	Final Version 1.0
--------------------	---	--------------------------

Primary Endpoints	SD^{a)}	Ratio	90% CI for the Ratio Based on N = 180	

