			Subjects With At Least 1 ALC <LLN^{b)} vs. Subjects With All ALC ≥LLN^{b)}	Subjects With At Least 2 ALC <LLN^{b)} vs. Subjects With All ALC ≥LLN^{b)}
CD4 T cell count		0.7	0.63, 0.77	0.63, 0.78
CD8 T cell count	0.35	0.8	0.72, 0.89	0.71, 0.91
		0.7	0.63, 0.78	0.62, 0.79
CD56 ^{bright} NK cell count	0.57	0.8	0.68, 0.95	0.65, 0.98
		0.7	0.59, 0.83	0.57, 0.86
T _{reg} count	0.95	0.8	0.60, 1.07	0.57, 1.12
		0.7	0.52, 0.93	0.50, 0.98

ALC = absolute lymphocyte count; CD = cluster of differentiation; CI = confidence interval; LLN = lower limit of normal; NK = natural killer; SD = standard deviation; T_{reg} = T regulatory; vs. = versus.

^{a)} Common standard deviation for the log-transformed change from Baseline.

^{b)} Up to Week 48.

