5.3.1 Analysis of the Primary Endpoint

The primary endpoints are the changes in lymphocyte subset counts for up to 48 weeks. The actual value, change and percent change from baseline in count and percent for each lymphocyte subset will be descriptively summarized at each applicable visit. Graphical display of median (Q1-25 percentile/Q3-75 percentile) of actual value and percent change from baseline in count and percent for each lymphocyte subset over time will also be presented. The Wilcoxon signed rank test will be used to test if the change and percent change from baseline in count and percent for each lymphocyte subset is different from zero. Listings of lymphocyte subsets will also be presented.

Furthermore, the primary endpoints will be summarized in various ALC subgroups to evaluate the nature of change in each subset in relation to the change in ALC.

ALC subgroups of interest include (1) subjects who have all ALC values \geq LLN ($0.91 \times 10^9/L$) up to Week 48, and (2) subjects who have at least 1 ALC value $<$ LLN over 48 weeks. A mixed model for repeated measures (MMRM) will be used to estimate the difference between ALC subgroups at each post-baseline visit up to Week 48. The model will be fitted with the change from baseline in count up to Week 48 for each of the TBNK lymphocyte subset as the dependent variable and will include ALC subgroup (all ALC values

CONFIDENTIAL

The information contained herein may not be used, disclosed, or published without the written consent of Biogen Idec MA Inc.

	Protocol 109MS310 An Open-Label Study to Assess the Effects of BG00012 on Lymphocyte Subsets in Subjects With RRMS	Final Version 1.0
---	---	--------------------------

\geq LLN up to Week 48; at least 1 ALC value $<$ LLN over 48 weeks), visit, corresponding Baseline counts, age, gender, and ALC subgroup-by-visit interaction as fixed effects. An unstructured variance-covariance matrix structure will be used in the MMRM model. Least squares (LS) mean, standard error, LS mean difference, 2-sided 95% confidence intervals (CIs) and p-values will be reported. Before the MMRM analysis, appropriate transformation may be performed based on the distribution of each TBNK lymphocyte subset parameter. The same analysis may be applied to other subsets.

Additional subgroups based on ALC values over time are defined:

- 1) ALC $< 0.5 \times 10^9/L$ for ≥ 6 months (24 weeks);

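### The signed-rank test on percent change over-rejects, almost always toward a false increase; it should be dropped or moved to the log ratio

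*SAP*

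**What the plan says.** Under the primary endpoint, SAP 5.3.1 plans: "The Wilcoxon signed rank test will be used to test if the change and percent change from baseline in count and percent" differs from zero, subset by subset. Two quantities are therefore tested, absolute change and percent change, each for counts and for percentage parameters.

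The SAP gives no significance level, symmetry condition or transformation for this test. A transformation is allowed only ahead of the MMRM. The nearest guide to a level is the MMRM output, where "2-sided 95% confidence intervals (CIs) and p-values will be reported". The same section also plots percent change over time as a median with quartiles.

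Protocol 16.2.2 takes a different position on testing: "There is no planned statistical hypothesis testing in this study". SAP 5.1 and 5.3 likewise call the analyses descriptive.

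The sample size table (SAP section 4, Table 3) works on the log scale. Its SD column is defined as "Common standard deviation for the log-transformed change from Baseline", with values 0.32 (CD4), 0.35 (CD8), 0.57 (CD56bright NK) and 0.95 (Treg).

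**The concern.** The signed-rank test ranks the absolute values and compares the ranks of rises with those of falls. It holds its level only if a rise and a fall of equal size are equally likely under no effect.

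Percent change cannot go below -100% but has no upper limit. A count that halves scores -50% and one that doubles scores +100%. On the log scale these are equal and opposite (-0.693 and +0.693), but on the percent scale the doubling gets the larger rank. Rises therefore outweigh falls even when nothing has changed on average.

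The study asks which subsets fall under treatment and which are spared. A test tilted upward can hide a fall in a variable subset or make an unchanged one look expanded. This is not a multiplicity problem: each single percent-change test is tilted, so adjusting the significance level across tests would not repair it.

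**Working it through.** **Inputs.** From SAP section 4: 180 evaluable subjects at Week 48, 200 enrolled, 10% discontinuation, a 76%/24% split by ALC, and the four log-scale SDs. Assumed: two-sided 5%, and a log-normal no-effect model, log(post/Baseline) ~ N(0, SD), so that the true median percent change is exactly zero.

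**The plan's own figures.** 180/0.9 = 200; 180 × 0.76 = 136.8 and 180 × 0.24 = 43.2, matching the stated 137 and 43. For the SD scale, take the CD4 row, "0.32 0.8 0.73, 0.88 0.71, 0.90": 1.645 × 0.32 × √(1/137 + 1/43) = 0.092, and 0.8 × exp(±0.092) gives 0.73 and 0.88, as printed. So the SDs are used as SDs of a log ratio. Not every limit in the table reproduces at 180 (12 to 14 of 32 match to two decimals; the largest gap is 0.019), but the SDs are inputs and are not affected. The SAP gives no error rate for the signed-rank test to reproduce.

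**Direction.** The test targets the median of pairwise averages. For two subjects with log ratios a and b, the average percent change (as a fraction) is exp((a+b)/2) × cosh((a−b)/2) − 1. The first factor has median 1 and the second is never below 1, so this median lies above zero. The tilt is upward.

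**Size under no effect.** Percent change is x = 100 × (exp(log ratio) − 1), and W is the sum of the ranks of |x| over x > 0. Then z = (W − n(n+1)/4)/√(n(n+1)(2n+1)/24). At n = 180 the mean is 180 × 181/4 = 8,145 and the SD is √(180 × 181 × 361/24) ≈ 700. Simulated with 20,000 to 60,000 replicates per cell:

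| Count (SD) | Percent change rejects | Called a decrease | Log ratio rejects |
|---|---|---|---|
| CD4 (0.32) | 17.0% | 0.2% | about 5% |
| CD8 (0.35) | 19.1% | 0.2% | about 5% |
| CD56bright NK (0.57) | 37.2% | 0.03% | about 5% |
| Treg (0.95) | 65.9% | 0.007% | about 5% |

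False increases make up 98.7% of rejections at SD 0.32 and 99.99% at SD 0.95. With exchangeable log-normal counts, the test on absolute change rejects in 4.7% to 5.2% of trials.

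**Range.**
- By n, over the four SDs: 7% to 20% at 43, 13% to 55% at 137, 18% to 71% at 200.
- At two-sided 10%, n = 180: 27% to 77%.
- Smaller SDs, n = 180: about 6% at 0.10, 7% at 0.15, 9% at 0.20, 13% at 0.25.
- Normal errors around a stable level (CV 10% to 25%): about 7% to 18%, again upward.
- Absolute change symmetric and independent of Baseline: about 5%.

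**True falls, n = 180.** Percentage of trials with a significant decrease on percent change, then on the log ratio:

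| Fall | CD4 | CD8 | CD56bright NK | Treg |
|---|---|---|---|---|
| 10% | 90 / 99 | 79 / 97 | 12 / 68 | 0.3 / 31 |
| 20% | 100 / 100 | 100 / 100 | 91 / 100 | 9 / 86 |
| 30% | 100 / 100 | 100 / 100 | 100 / 100 | 61 / 100 |

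For Treg with a 10% fall, percent change shows a significant increase in about 17% to 18% of trials; at a 20% fall this drops below 1%.

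**Disagreement with the count-change test.** Under no effect with exchangeable log-normal counts, percent change shows a significant increase while absolute change is non-significant in about 14% (CD4), 35% (CD56bright NK) and 64% (Treg) of trials.

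**The case against.** The affected p-value has a minor role. The primary endpoint is change in counts. The same sentence tests absolute change, which holds its level, and the modelled analysis is an MMRM on change in count. No success rule depends on the percent-change p-value, and quartile plots of percent change will sit beside it. All of this stands, and it limits the severity.

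The rates also rest on planning SDs whose source is not stated. If they come from treated subjects, they include variation in drug response, and no-effect variability could be smaller. This stands too: at SD 0.10 to 0.20 the rate is about 6% to 9%. It changes the size of the error, not its direction.

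Exchangeability of Baseline and later counts is not guaranteed. Exclusion 7 removes confirmed low screening ALC, and earlier disease-modifying therapies stop at entry without a required washout (Protocol 8.2). Such drift could shift any test against zero, including the log ratio; it does not rescue percent change.

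A reader might infer that real falls in general will be missed or called increases. The simulations do not support that. Falls of 20% or more in CD4, CD8 and CD56bright NK are detected in 91% to 100% of trials, and Protocol 5.3.2 reports mean lymphocyte counts about 30% lower after a year. Wrong-direction calls under a true fall of 10% or more are material only for Treg at the smaller fall. Nor does the percent-change p-value always conflict with the count-change one: no simulated trial had the two significant in opposite directions.

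**Conclusion.** The point holds and should be fixed. Under the log-scale model that Table 3 implies, the percent-change signed-rank test has a false-positive rate of about 17% to 66% for the four counts with a stated SD, at n = 180 and two-sided 5%. The level is an assumption, and the rate falls toward 5% with smaller SDs, smaller groups or an additive model independent of Baseline. The error is almost always, not always, toward an increase.

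The practical loss is in high-variance subsets: Treg above all, and CD56bright NK for small falls. No rate is shown for the percentage-of-parent parameters or for counts without a stated SD.

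It would be tempting to read this as an invalid primary analysis. The documents do not support that: the analyses are descriptive and the count-change test is sound. The consequence is misleading p-values, some at odds with the count-change p-value for the same subset and visit.

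**What to change.** In SAP 5.3.1, delete the signed-rank test on percent change. If a relative-change test is wanted, apply it to log(post/Baseline) and state a rule for zero counts. Keep the test on absolute count change. Report percent change as median with Q1/Q3 only, without a p-value; SAP 5.1 does not list quartiles among the default summaries, so they need adding for this variable.

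The cost is about a sentence of SAP text and a small programming change. No new data are needed. In the simulations the log-ratio test returned the false-positive rate to 4.9% to 5.3%.

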2 STUDY DESIGN

2.1 Study Overview

This is an open-label, multicenter study to evaluate the effects of BG00012 on lymphocyte subtypes and Ig isotypes. Approximately 200 subjects were treated in approximately 100 sites in North America and Europe.

After the Screening Visit (up to 28 days) if required per local guidelines and if not already available within the previous 3 months, a magnetic resonance imaging (MRI) scan should be performed locally before starting therapy with BG00012 as per local guidelines. Subjects will then receive BG00012 treatment for 96 weeks (Treatment Period). Blood samples for lymphocyte subset analysis, as well as blood samples for the determination of each subject's complete blood count with differential, will be collected at Screening, Baseline (Day 1), and Weeks 4, 8, 12, 24, 36, 48, 60 (complete blood count [CBC only]), 72, 84 (CBC only), and 96. Clinical samples for the analysis of blood chemistries will be collected at Screening, Baseline (Day 1), and Weeks 4, 8, 24, 48, and 96. A post-treatment follow-up visit, at which safety assessments will be performed, will occur 4 weeks after the final dose of BG00012.

Subjects who temporarily withhold or permanently discontinue study treatment for any other reason than lymphopenia and have a lymphocyte count <LLN will continue protocol-required visits and assessments and will also be followed every 4 weeks for 24 weeks, then every 12 weeks (unless clinically indicated more often or at the Investigator's discretion) until the lymphocyte count is \geq LLN or for up to 48 weeks following drug discontinuation, whichever occurs sooner.

Subjects who develop a confirmed lymphocyte count of <500 cells/mm³ at any time during the study will be monitored every 4 weeks. If the lymphocyte count stays <500 cells/mm³ for 24 weeks, the subject will temporarily withhold study treatment. If the lymphocyte count does not recover to LLN within 24 weeks while study treatment is temporarily withheld, study treatment will be discontinued permanently.

CONFIDENTIAL

The information contained herein may not be used, disclosed, or published without the written consent of Biogen Idec MA Inc.

	
Protocol 109MS310 An Open-Label Study to Assess the Effects of BG00012 on Lymphocyte Subsets in Subjects With RRMS
	Final Version 1.0
---	---	--------------------------

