5.3 Pharmacodynamics

The pharmacodynamic analysis will be based on data from the pharmacodynamic population as defined in [Section 5.1](#). The pharmacodynamic data includes the lymphocyte subsets, ALC, and isotypes (including IgA, IgM, IgG and IgG subclasses). A listing of reportable lymphocyte subset parameters are available in [Appendix 1](#). The lymphocyte subsets are categorized into the following eight groups:

- TBNK lymphocyte subsets
- T cell subsets
- B cell subsets
- Myeloid and NK cell subsets
- Intracellular T cell cytokines
- VLA-4/LFA-1 expression
- [REDACTED]
- [REDACTED]

Statistical analyses will be [REDACTED] and descriptive in nature, with appropriate measures of precision provided where applicable.

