5.7 Changes in statistical analysis methods

5.7.1 Change in clinical assessment population definition

In protocol, the evaluable population for clinical assessments is defined as all subjects who receive at least 1 dose of study treatment and at least 1 measurement for each of the clinical assessments after Baseline. [REDACTED]

[REDACTED]

[REDACTED]

CONFIDENTIAL

The information contained herein may not be used, disclosed, or published without the written consent of
Biogen Idec MA Inc.

biogen idec	Protocol 109MS310 An Open-Label Study to Assess the Effects of BG00012 on Lymphocyte Subsets in Subjects With RRMS	Final Version 1.0
--------------------	---	--------------------------

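### The SAP adds undeclared signed-rank tests and MMRM p-values to a study whose protocol plans no testing, and the percent-change test is not a valid test of no change

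*SAP*

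**What the plan says.** Protocol 16.2.2 describes the pharmacodynamic analyses as descriptive, with measures of precision, and adds: "There is no planned statistical hypothesis testing in this study". For the mixed model, Protocol 16.2.2.1 promises point estimates and 90% confidence intervals and mentions no p-values. SAP section 4 repeats that the sample size rests on precision of estimation and not on formal testing.

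SAP 5.3.1 first provides that values and changes "will be descriptively summarized at each applicable visit". It then adds: "The Wilcoxon signed rank test will be used to test if the change and percent change from baseline in count and percent". The null value is zero, and every subset is covered. Later in the same section the mixed model (MMRM) comparing ALC subgroups is to report 95% intervals and p-values.

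SAP 5.3 defines the scope: "The lymphocyte subsets are categorized into the following eight groups", with the parameters listed in Appendix 1. Two of the eight groups are redacted.

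The only change from the protocol visible in SAP 5.7 is headed "Change in clinical assessment population definition". Part of that section is redacted, so this describes the visible text only.

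**The concern.** Three things are wrong together.

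- **Undeclared testing.** The protocol says there are no tests. The SAP introduces two kinds (signed-rank and MMRM) on the primary endpoint without visibly recording the departure. The visible text gives no alpha, no multiplicity adjustment, no statement that the p-values are nominal, and no lead subset or visit.
- **No interval for the primary quantity.** The primary endpoint is the change in subset counts. For the overall within-subject change, SAP 5.1 and 5.3.1 plan n, mean, SD, median, range and quartile plots, but no confidence interval. The MMRM intervals concern ALC-subgroup means and differences, and are committed only for the TBNK panel. The one inferential statement about overall change is therefore a p-value, although the protocol's stated aim is precision.
- **A test on an unsuitable scale.** The signed-rank test takes symmetry about zero as its null. Percent change cannot fall below -100% but has no upper limit, so for skewed counts it is not symmetric about zero even when nothing has changed.

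The stake is the study report. It could present many nominally significant subset changes from tests the protocol says do not exist, some of them produced by the scale alone.

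**Working it through.** **1. Parameters.** The documents state no number of tests, so there is no figure of the plan's own to reproduce. Counting the visible rows of SAP Appendix 1:

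| Group | Counts | Percents | MESF | Total |
|---|---|---|---|---|
| TBNK | 8 | 8 | 0 | 16 |
| T cell | 28 | 28 | 0 | 56 |
| B cell | 8 | 8 | 0 | 16 |
| Myeloid and NK | 8 | 8 | 0 | 16 |
| Intracellular cytokines | 0 | 16 | 0 | 16 |
| VLA-4/LFA-1 | 0 | 14 | 14 | 28 |
| **Sum** | **52** | **82** | **14** | **148** |

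The test sentence covers counts and percents. The 14 MESF rows are fluorescence intensities and are neither, which leaves 52 + 82 = 134.

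**2. Visits.** SAP 2.1: samples "will be collected at Screening, Baseline (Day 1), and Weeks 4, 8, 12, 24, 36, 48, 60" and later, with Week 60 for blood count only. Subsets therefore have six post-baseline visits to Week 48 (4, 8, 12, 24, 36, 48). Weeks 72 and 96 make eight.

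**3. Number of signed-rank tests** = parameters x 2 scales x visits. Expected nominal positives = tests x 0.05. The 0.05 is my assumption, and so is no true change in any parameter.

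| Reading | Tests | Expected positives |
|---|---|---|
| Count and percent, six visits | 134 x 2 x 6 = 1,608 | 80.4 |
| Same, without VLA-4/LFA-1 | 120 x 2 x 6 = 1,440 | 72.0 |
| Counts only, six visits | 52 x 2 x 6 = 624 | 31.2 |
| Count and percent, one time point | 134 x 2 x 1 = 268 | 13.4 |
| Count and percent, eight visits | 134 x 2 x 8 = 2,144 | 107.2 |

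Correlation between tests does not alter these expectations. It does mean that the number of separate questions is well below the number of p-values.

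**4. MMRM p-values.** The 8 TBNK counts x 6 visits give 48 more if each visit difference is tested.

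**5. Validity of the percent-change test.** Let d be the log ratio of post-baseline to baseline. Percent change is 100(e^d - 1). A doubling scores +100 and a halving scores -50, although the two are equal and opposite on the log scale. Increases therefore take the larger ranks and the statistic leans towards an increase.

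I simulated no change under these conditions:
- n = 180, the plan's evaluable number.
- Baseline and post-baseline values exchangeable and lognormal.
- SD of d taken from Protocol Table 6 (SAP Table 3), read as the SD of the log ratio.
- Shared between-subject log-SD assumed to be 0.5.
- Two-sided 0.05 with the normal approximation, 20,000 datasets per row.

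| Subset | SD of d | Absolute change rejects | Percent change rejects |
|---|---|---|---|
| CD4 T cells | 0.32 | 5% | 17% |
| CD8 T cells | 0.35 | 5% | 19% |
| CD56bright NK | 0.57 | 5% | 37% |
| Treg | 0.95 | 5% | 66% |

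Separate runs differ by a point or so (16% to 18% for CD4, 65% to 66% for Treg). Setting the shared log-SD to 0.3 or 0.8 leaves the picture unchanged, because under this model percent change depends only on d. A signed-rank test on the log ratio itself also rejects in about 5%.

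**The case against.** The best case for the SAP is that this is a single-arm, descriptive study with no success criterion, and no decision hangs on any p-value. Medians and quartiles are shown over time, so effect sizes stay visible, and multiplicity adjustment in such a setting is largely a matter of taste. The word that qualifies the analyses alongside descriptive is redacted in both documents, so the sponsor's own label cannot be fully read. Most of this stands. It argues for labelling the p-values and against formal error control. It does not answer the conflict with the protocol, the missing interval, or the percent-change problem.

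Several stronger readings are tempting but unsupported.

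- **At least 1,776 tests.** A reader who multiplies all 148 visible rows by two scales and six visits gets 1,776, but this is not a floor. It includes the 14 MESF rows. It counts VLA-4 assays that the schedule footnote (SAP Table 1, footnote 7) makes optional. It also assumes testing at every visit, which the test sentence does not say; the by-visit wording belongs to the earlier summary sentence.
- **About 80 false positives expected in this trial.** That needs no change in any parameter. Protocol 5.3.2 reports mean lymphocyte counts falling by about 30% after one year, so a global null is implausible for the counts.
- **Noisy rare subsets generate false positives in themselves.** For absolute change they do not. A valid signed-rank test keeps its level at any noise, and noise costs power. The excess arises only on the percent scale.
- **Confidence intervals would remove multiplicity.** They would not. With one scale, 134 x 6 = 804 intervals at 90% would give 804 x 0.10 = 80.4 excluding zero by chance if nothing changed. The gain is in reporting size and precision.

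**Conclusion.** The point holds in this form. SAP 5.3.1 contradicts Protocol 16.2.2 by adding signed-rank tests on two scales for every subset, together with MMRM p-values. The departure is not visibly declared in SAP 5.7, and the p-values have no stated alpha, adjustment or nominal label.

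The number of signed-rank tests depends on the reading: about 1,608 for visible count and percent parameters at six visits, 624 for counts only, and 268 at one time point. Each is in the hundreds or more. The redacted groups and later visits could add to it. The figure of about 80 nominal positives is a scale marker that rests on an assumed 0.05 and no true change.

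The percent-change test should go whatever is decided about the rest. Its null rejection of roughly 16-17% (CD4) to 65-66% (Treg) rests on an assumed exchangeable lognormal model and on reading the tabulated SDs as SDs of the log ratio. The exact rates would differ under other skewed distributions. The cause, asymmetry of percent change, would remain.

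Nothing here shows that the primary conclusions would be wrong, and the descriptive summaries are unaffected.

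**What to change.** 1. Delete the signed-rank tests from SAP 5.3.1. Remove the percent-change test in any case; percent change can still be summarized descriptively.
2. For each subset and visit, report either the median (Hodges-Lehmann) change or the back-transformed mean log ratio, with a confidence interval. If the log ratio is chosen, state how zero counts in rare subsets are handled.
3. Use one stated confidence level throughout, reconciling the protocol's 90% for the MMRM with the SAP's 95%, and record the choice in SAP 5.7.
4. If any signed-rank tests or the MMRM p-values are kept, declare them in SAP 5.7 as a change from Protocol 16.2.2, state the visits and the scale, and label them nominal and exploratory. Removing only the signed-rank tests would leave the conflict in place through the MMRM p-values.

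The cost is SAP wording and revised table shells, with no change to data collection or trial conduct. The downside is losing nominal p-values for publication.

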16.2.2.1. Analysis of the Primary Endpoint

Counts and change from Baseline in counts for each of the lymphocyte subsets will be descriptively summarized at each applicable visit. Furthermore, the primary endpoints will be summarized in various ALC subgroups to evaluate the nature of change in each subset in relation to the change in ALC. Additionally, a mixed model for repeated measures (MMRM) will be used, which will be fit with the change from Baseline for each of the lymphocyte subsets as the dependent variable and will include ALC subgroups, visit, corresponding Baseline counts, age, gender, and ALC groups-by-visit interaction as fixed effects to estimate the difference between ALC subgroups. Point estimates and 2-sided 90% confidence intervals (CIs) will be derived from the model. Appropriate transformation may be performed based on the distribution of data.

[figure not shown]
ALC subgroups of interest include (1) subjects who have all ALC values \geq LLN up to Week 48, (2) subjects who have at least 1 ALC value $<$ LLN over 48 weeks, and (3) subjects who have at least 2 ALC values $<$ LLN over 48 weeks. Additional subgroups will be further defined in the Statistical Analysis Plan.

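### The subgroup MMRM defaults to raw count changes, although the sample size rests on log-scale ratios; if the raw scale is kept, its CIs run about 12-20% too wide under Table 3's own assumptions

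*SAP*

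**What the plan says.** **Analysis.** SAP 5.3.1 defines the model for the contrast between subjects with all ALC values at or above LLN and those with at least one value below it: "The model will be fitted with the change from baseline in count up to Week 48 for each of the TBNK lymphocyte subset". On the covariance it says only: "An unstructured variance-covariance matrix structure will be used in the MMRM model". No separate matrix per ALC subgroup is mentioned, so pooling across subgroups is the ordinary reading, although the SAP does not state it. The output is: "Least squares (LS) mean, standard error, LS mean difference, 2-sided 95% confidence intervals (CIs) and p-values will be reported". No ratio and no back-transformation is named.

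**Transformation.** The same paragraph adds: "Before the MMRM analysis, appropriate transformation may be performed based on the distribution of each TBNK lymphocyte subset parameter". Protocol 16.2.2.1 is equally open: "Appropriate transformation may be performed based on the distribution of data". Neither document names the log or gives a rule for deciding.

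**Planning.** SAP section 4 and Protocol 16.7 base the sample size on how precisely ratios between ALC subgroups are estimated. The SDs in SAP Table 3 (Protocol Table 6) carry the footnote "Common standard deviation for the log-transformed change from Baseline".

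**Reach.** The committed model covers the TBNK subsets. For the rest, the SAP says: "The same analysis may be applied to other subsets".

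**The concern.** Planning and analysis are on different scales. Table 3 promises a given precision for a ratio. The default model gives a difference in cells/mm³, for which no planning precision is stated.

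The scale also affects the standard error. If the SD is common on the log scale, the raw SD is proportional to the level of the count, so it is smaller in the group whose counts fall further. That is the low-ALC group, which is also the smaller one. A pooled covariance then lets the larger, more variable group set the variance for the smaller group, and the standard error of the contrast comes out too large.

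The transformation clause leaves this open. As it works parameter by parameter, CD4 could be reported in cells and CD8 on a log scale in the same table. The scale of a contrast that carries p-values would also be chosen after seeing the data. This MMRM is the only model that the SAP commits to for comparing ALC subgroups on the primary endpoint.

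**Working it through.** **Inputs** (SAP section 4 and Table 3): 180 evaluable subjects; 76% = 137 with all ALC values at or above LLN; 24% = 43 with at least one value below; true ratio r = 0.8 or 0.7; log SD 0.32 (CD4) and 0.35 (CD8).

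**Step 1: reproduce the plan's figure.** On the log scale the 90% limits are r × exp(±1.645 × SD × √(1/43 + 1/137)), and √(1/43 + 1/137) = √0.03056 = 0.1748.

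- CD4, r = 0.8: half-width 1.645 × 0.32 × 0.1748 = 0.0920, giving 0.730 to 0.877. Table 3 states 0.73, 0.88.
- With 29 subjects (16% of 180) for the at-least-two column, all 32 limits in Table 3 agree within 0.02. Many do not match to the second decimal, and the stated intervals are mostly slightly wider.

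Table 3 is therefore a log-scale calculation with a common SD.

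**Step 2: carry the same assumptions to the raw scale.** With equal baselines, a common log SD makes the low-ALC group's raw SD r times the other group's. Set the other group's raw variance to 1.

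- Pooled variance: v = (136 + 42r²)/178
- Squared SE that the pooled model reports: v × (1/43 + 1/137)
- Correct squared SE: r²/43 + 1/137

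| r | v | Pooled SE² | Correct SE² | SE ratio | Coverage of nominal 95% CI |
|---|---|---|---|---|---|
| 0.8 | 0.915 | 0.02796 | 0.02218 | √1.260 = 1.12 | 97.2% |
| 0.7 | 0.880 | 0.02688 | 0.01869 | √1.438 = 1.20 | 98.1% |

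Coverage is 2Φ(1.96 × SE ratio) − 1. The SE ratio does not depend on the confidence level, so the change from 90% CIs in Table 3 to 95% in SAP 5.3.1 is a separate matter.

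**Step 3: check by simulation.** A single-visit model of raw change on baseline and subgroup was simulated with 43 versus 137 subjects. The baseline log SD of 0.35 and a common decline to 0.8 of baseline are assumptions, not document figures. Across Table 3's four SDs and both ratios:

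- Raw scale, equal baselines: excess 8-19%.
- Raw scale, low-ALC group's baseline assumed 20% lower: excess 21-36%.
- Log scale: model SE over empirical SE 1.00-1.03, so no systematic excess.

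**Step 4: relax the common log SD.** If the low-ALC group's log SD is 1.1 times the other's (assumption), its raw SD at r = 0.8 is about 0.88 of the other's and the excess falls to about 7%. It vanishes when the log SD is 1/0.8 = 1.25 times larger (r = 0.8) or 1/0.7 = 1.43 times larger (r = 0.7).

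**The case against.** The strongest reply is that the plan already allows the remedy: "appropriate transformation may be performed based on the distribution of each TBNK lymphocyte subset parameter". If counts are close to lognormal, a look at the distribution points to the log. The excess width then disappears and a ratio can be obtained. This stands to the extent that the consequence is conditional: a reader might infer that the intervals will be too wide and that no ratio can be had, and the documents do not support that. It does not remove the point, because the clause sets no rule and promises no back-transformation.

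Other replies also carry weight:

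- The error is conservative, the study is descriptive, and Protocol 16.2.2 plans no hypothesis testing. The SAP nevertheless reports CIs and p-values from this model.
- The primary endpoint is the change in subset counts, so a difference in cells is a legitimate scale. Percent change is also summarised descriptively by ALC subgroup. Neither gives the modelled ratio with a CI that Table 3 plans for.
- The common log SD is a planning simplification, and no document gives SDs by subgroup. Step 4 shows how quickly the excess shrinks if it fails.
- Pooling is inferred from the SAP's silence, although it is the usual default.
- Appendix 1 places CD56bright NK cells and Treg outside the TBNK group, so a reader who applies the point to all four rows of Table 3 goes too far.

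**Conclusion.** The concern holds as a mismatch of scale that the plan leaves unresolved. The default model estimates a difference in raw counts, while the sample size is justified by ratios with a common log SD, and nothing commits the analysis to the planning scale.

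If the raw scale is kept, the SE and CI for the subgroup contrast are about 12% (ratio 0.8) to 20% (ratio 0.7) too wide, and a nominal 95% CI covers about 97-98%. This rests on Table 3's own assumptions (43 versus 137, common log SD), on equal baselines, and on a covariance pooled across subgroups. CD4 and CD8 are the rows of Table 3 directly affected.

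A reader might infer an excess of 30% or more, reasoning that subjects who start near LLN cross it more easily. The direction is plausible, but that size needs a lower baseline in the low-ALC group, and the documents give no baseline by subgroup. Nor does the point show the sample size to be wrong: Table 3 reproduces closely on the log scale.

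**What to change.** In SAP 5.3.1, pre-specify log(count) minus log(baseline count) as the dependent variable of the TBNK count MMRM, with log baseline count as the covariate in place of the raw count. Report the subgroup contrast as a back-transformed ratio with its CI. Apply the same rule to any other subset count to which the model is extended. Replace the optional transformation sentence with this. Raw-count and percent changes stay in the descriptive summaries.

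The cost is SAP wording, with two small downsides. Zero counts need a stated offset rule; they should be rare for TBNK counts, but the rule needs more thought for sparse subsets in Appendix 1 such as plasmablasts. The modelled contrast is also read as a ratio rather than in cells/mm³.

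Keeping the raw scale with a separate covariance matrix per subgroup is a weaker alternative. Six post-baseline visits to Week 48 need 6 × 7/2 = 21 covariance parameters per subgroup, with about 43 low-ALC subjects to estimate them. It should not be relied on without a plan for non-convergence.
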